3.5.5.4 Predictive Biomarker Analyses

MEL Patients

To address the primary predictive biomarker hypothesis in the MEL population, the following two-step approach will be implemented: 1) estimation of a cutoff point for PD-L1 expression level based on a training set of melanoma patients, and 2) application of the cutoff point to prospectively test the biomarker hypothesis (i.e., formal validation of the cutoff point). The training set consists of patients from the cohort B enrolled through Amendment 04, including 20 ipilimumab-naïve patients at 2 mg Q3, 22 ipilimumab-naïve patients at 10 mg Q3, 41 ipilimumab-naïve patients at 10 mg Q2, 32 ipilimumab-treated patients at 10 mg Q3, and 16 ipilimumab-treated patients at 10 mg Q2. Once the cutoff point is estimated, it will be applied to the analysis of randomized patients in Part B and Part D.

The cutoff point determination process is blinded to the validation analyses to ensure they have the necessary scientific rigor and integrity to confirm a clinical benefit of pembrolizumab (MK-3475) in the "biomarker positive" patients.

Estimation of cutoff point

All patients in the training set are required to have new biopsies such that we expect the yield of tumor samples available for PD-L1 analysis to be very close to the number of patients enrolled. All tumors will be tested retrospectively, with the test operators blinded to all clinical data. Four scoring systems will be evaluated initially: one based on H-score, the other three based on the percentage of tumor cells expressing PD-L1 with minimum intensities of 1+, 2+, and 3+, respectively. The latter two scoring systems (percentage of tumor cells with minimum intensities of 2+ or 3+) may be abandoned if the operators determine that they are too difficult to score.

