Kendall's tau statistic along with a one-sided p-value will be provided for testing the concordance between maximum total tumor volume reduction (%) produced by pembrolizumab (MK-3475) and PD-L1 expression levels in tumor tissue [20]. Kendall's tau statistic is rank based. For the supportive analysis, those without a post-treatment disease assessment (presumably mainly due to discontinuation before week 12) will be assigned a lower rank (equivalent to less tumor reduction) than those with a post-treatment disease assessment. They will further be ranked by category of reasons for discontinuation (death, disease progression by RECIST 1.1 per central review and other reasons) in ascending order, and among each category they will be ranked by time to

discontinuation, the earlier the lower. Supportive analysis will be performed assessing the concordance between response by RECIST 1.1 per central review and PD-L1 expression.

Receiver operating characteristic (ROC) analysis will be generated for each scoring system. The cutoff point will be chosen by statistical estimation of Youden Index assisted with visual inspection from the ROC. In addition, the following two confounding categorical variables will be evaluated to determine whether or not they can be used to further improve the scoring system: “stroma pattern” (presence or absence of a band mononuclear inflammatory cells expressing PD-L1, in the stroma adjacent to tumor nests) and “dendritic pattern” (presence or absence of a lattice of dendritic cells expressing PD-L1, within tumor nests). Once the final scoring system and cutoff point is chosen, it will be documented before validation can be conducted.

Validation

Tumor samples from patients in the validation sets will be sent to a third party contract research organization (CRO) for re-identification. The CRO will remove old identifying information from each sample and replace it with a new identifier. The samples will then be sent to the clinical laboratory sites for analysis. Thus, both Merck and the laboratories will be blinded to the linkage between PD-L1 test result and the clinical outcome. The third-party CRO will release the key containing the old versus new identifiers to Merck only after database lock.

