3.5.6 Multiplicity

A Hochberg procedure will be applied to final analysis of RR and DCR for internal decision purposes based on the ipilimumab-naïve patients treated at 10 mg/kg in Part B enrolled through Amendment 4. The overall type I error rate is set at 5% (one-sided),

i.e., the trial is considered to have reached the efficacy objective if the two corresponding p-values for testing the null hypothesis (RR=10% and DCR=30%) are less than 5% OR either one is less than 2.5%. There are two planned interim analyses for administrative purposes. There is no intention to terminate the study early for efficacy, and no multiplicity adjustment is applied to the interim analyses.

The predictive biomarker hypothesis on concordance between tumor volume change and PD-L1 will be formally tested at a type I error rate of 2.5% (one-sided) separately for each part of the study, irrespective of the outcome from efficacy analyses. Once the null hypothesis is rejected, a step-down procedure may be applied to the testing of other biomarker hypotheses prospectively specified before the end of the study. While additional exploratory analyses will be conducted to evaluate alternative predictive biomarkers, there is no multiplicity control of such analyses and no formal conclusion can be made.

The efficacy hypothesis on anti-tumor activity of pembrolizumab (MK-3475) is tested at 5% (one-sided) for Part B ipilimumab-treated (non-randomized), at 10% (one-sided) for Part C, and at 2.5% (one-sided) for all other populations. Between-dose comparisons are all conducted at 20% (two-sided), or equivalent 10% (one-sided) for sample size and power calculation purpose below, except for Part B (10 mg/kg Q3W vs 10 mg/kg Q2W) which is conducted at 5% (two-sided).

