If Part F data show no evidence that line of therapy (1L vs 2L+) impacts efficacy, data will be combined across line of therapy and within dose for more powerful assessment of difference in RR between the two dose schedules and for more precise estimation of RR at a dose schedule. The pooled analysis will be conducted in the overall biomarker positive population as well as in the strongly biomarker positive population, as appropriate.

PD-L1 biomarker effect

Kendall's tau statistic will be used for testing the PD-L1 biomarker effect for various tumor and treatment groups. All testing will be conducted at type I error rate of 2.5% (one-sided). For a sample size of approximately 45 patients with both post-treatment disease assessments and valid evaluation of baseline PD-L1 expression levels in newly obtained tumor biopsies, the study has approximately 90% power to detect a one-fold

difference in concordance (i.e., odds of concordance relative to discordance = 2, or in other words tumor is twice more likely to reduce than to increase if the patient's tumor has high expression of the PD-L1 than low expression). When the sample size is reduced to 25 patients, Kendall's tau has 90% power to detect a 1.5 to 2-fold difference in concordance. In addition, the Youden index and other methods will be used for biomarker cut-off point analysis.

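### The plan does not tie the formal 2.5% PD-L1 concordance test to one locked score in validation patients; if the test is run in the patients used to choose the score, its error exceeds 2.5%.

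*Combined protocol and SAP*

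**What the plan says.** **Choice of score.** Section 3.5.5.4 sets out two steps for melanoma: estimate a cutoff in a training set, then validate it in other patients. The training set is Part B through Amendment 04. In it, "Four scoring systems will be evaluated initially: one based on H-score, the other three based on the percentage of tumor cells expressing PD-L1" at minimum intensities of 1+, 2+ and 3+. The 2+ and 3+ scores can be dropped if the readers, who are blinded to clinical data, find them too hard to score. An ROC curve is drawn for each score. "The cutoff point will be chosen by statistical estimation of Youden Index assisted with visual inspection from the ROC". Stroma and dendritic staining patterns may then be used to refine the score. The final score and cutoff are documented before validation starts.

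**The test.** Section 3.5.2 defines the primary biomarker hypothesis as concordance between baseline PD-L1 and maximum tumor volume reduction. The Kendall's tau procedure for testing it, including how patients without a post-treatment assessment are ranked, appears in Section 3.5.5.4 under the estimation step. The validation text compares response rate, disease control rate and other endpoints above and below the cutoff, and adds a logistic regression. It does not mention tau.

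**Error rate and use.** Section 3.5.6 says the concordance hypothesis "will be formally tested at a type I error rate of 2.5% (one-sided) separately for each part of the study". Rejection may open a step-down to other biomarker hypotheses. Section 3.5.9 makes confirmed concordance a condition for a biomarker-positive analysis in ipilimumab-naïve patients, should the all-comer objective be missed. Section 3.5.7 gives power for the tau test across tumor and treatment groups, but does not say which patients or which score.

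**The concern.** Kendall's tau depends on how the score ranks patients, not on where the cutoff is placed. So the choice of score matters for its error rate. A reader who follows the text would run the test where it is described: in the patients whose outcomes help to choose among the scores. A single 2.5% level then no longer bounds the chance of a false positive finding.

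That finding acts as a gate. The training list in Section 3.5.5.4 includes 22 + 41 = 63 ipilimumab-naïve patients at 10 mg/kg. The score choice, the cutoff, the gate test and the gated analysis in Section 3.5.9 could therefore all use largely the same patients.

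The question also arises for lung cancer. Part C is a single arm whose data feed the NSCLC cutoff by the same estimation methods. It has no validation patients of its own, yet a test for each part would include it.

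**Working it through.** **1. Reproduce the stated power.** Inputs from Section 3.5.7: "For a sample size of approximately 45 patients with both post-treatment disease assessments and valid evaluation" of PD-L1; "the study has approximately 90% power to detect a one-fold" difference, which the plan explains as "odds of concordance relative to discordance = 2"; level 2.5% one-sided.

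- tau = (odds − 1)/(odds + 1) = (2 − 1)/(2 + 1) = 0.333
- Null standard error = √[2(2n + 5)/(9n(n − 1))] = √[2 × 95/(9 × 45 × 44)] = 0.1033
- Power = Φ(0.333/0.1033 − 1.960) = 89.8%, against about 90% stated

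For 25 patients the plan states "90% power to detect a 1.5 to 2-fold difference in concordance". The standard error is 0.1427, so 90% power needs tau = (1.960 + 1.282) × 0.1427 = 0.463. That is odds of 1.463/0.537 = 2.72, a 1.72-fold difference, inside the stated range. Both figures are those of one test with one score.

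**2. Error if any of k scores may count.** With independent scores it is 1 − 0.975^k. With a common correlation ρ between the test statistics it is 1 − ∫ φ(g) [Φ((1.960 − √ρ g)/√(1 − ρ))]^k dg. The documents give no ρ, so the values below are assumptions. k = 4 is the full list; k = 2 leaves H-score and the 1+ percentage.

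| ρ | k = 4 | k = 2 |
|---|---|---|
| 0 (independent) | 9.6% | 4.9% |
| 0.50 | 7.8% | 4.5% |
| 0.70 | 6.5% | 4.2% |
| 0.80 | 5.7% | 3.9% |
| 0.90 | 4.7% | 3.5% |
| 0.95 | 4.0% | 3.2% |
| 0.97 | 3.6% | 3.1% |

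**3. Simulation at the training-set size.** The training list adds up to 20 + 22 + 41 + 32 + 16 = 131. Outcome was simulated independently of PD-L1, with nested percentage scores plus H-score under several illustrative staining models.

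- Any of four scores significant: 3.9% to 6.1%.
- Either of two scores significant: 2.2% to 3.2%. With 4,000 trials the Monte Carlo standard error at 2.5% is √(0.025 × 0.975/4,000) = 0.25 percentage points, so the lower values cannot be told apart from 2.5%. H-score and the 1+ percentage were almost interchangeable in these models.
- Only the score with the best Youden index tested, with an assumed response threshold: about 2.6% to 3.9%.

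The effect of the stroma and dendritic refinements was not computed.

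**4. Validation patients.** A score fixed beforehand and tested once in patients who played no part in choosing it keeps its 2.5% level.

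**5. Price of adjusting in training data.** Bonferroni over four scores tests each at 0.025/4 = 0.625% (critical value 2.498).

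- n = 45, odds 2: Φ(0.333/0.1033 − 2.498) = about 77%, down from 89.8%
- n = 131, odds 2: standard error 0.0590; Φ(0.333/0.0590 − 2.498) = above 99%

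**The case against.** A reader might infer that the concordance test has a true error of 3.6% to 6.5%. The documents do not support that, for these reasons:

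- **Selection rule.** The range is the chance that any of four tests is significant. The plan does not pick the score with the smallest tau p-value; it uses ROC curves and the Youden index, which inflated the error less in simulation.
- **Number of scores.** Two scores may be dropped for feasibility by readers blinded to outcome. That is not an outcome-driven choice, and it lowers the range.
- **Validation set.** The plan provides separate randomized Part B and Part D patients, a score and cutoff documented first, and blinding of the sponsor and laboratories to the PD-L1 and outcome link until database lock. It describes the second step as the prospective test of the biomarker hypothesis. Part D contains no melanoma training patients.
- **Consequence.** The Section 3.5.9 gate opens only an exploratory analysis, and only if the all-comer objective is missed, in a population analyzed for the sponsor's internal decisions. The step-down in Section 3.5.6 is optional and limited to hypotheses specified before the study ends.

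All of this stands and narrows the size of the point. It does not close the gap. Section 3.5.6 never assigns the tau test to the validation patients, and the validation text tests other quantities. Neither says which score is meant.

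**Conclusion.** The point holds as a gap in the testing rule, conditional in its size. The plan gives one 2.5% level, several candidate scores compared against outcome and no adjustment. If the formal test is run in the training patients, its error exceeds 2.5%: about 3.6% to 6.5% for any of four scores and about 3.1% to 4.2% for two, both at assumed correlations of 0.97 to 0.70, and roughly 2.6% to 3.9% if only the Youden-chosen score is tested, under illustrative models. With two nearly identical scores the excess may be negligible.

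No inflation applies to Part D, or to any validation patients tested with the locked score. If training and randomized Part B patients were pooled, the inflation would be smaller than in the training set alone. This is a cheap improvement that settles an open question, not evidence that the plan's biomarker validation is unsound.

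**What to change.** In Sections 3.5.5.4 and 3.5.6, state that the formal 2.5% Kendall's tau test, and any step-down from it, uses the single documented score in validation patients: randomized Part B and Part D for melanoma, randomized Part F for NSCLC. Section 3.5.5.4 sets aside half of the Q2W patients in Part F to train a Q2W-specific cutoff; that half should not count as validation for that schedule.

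Treat tau p-values from training patients (Part B through Amendment 04, and Part C) as descriptive. Alternatively, apply Hochberg or Bonferroni across the scores tested there. Reword the gate in Section 3.5.9 so that it refers to whichever of these is adopted.

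**Cost.** The Part B training-set and Part C tests lose formal status or use a stricter level. Under Bonferroni over four scores, power at concordance odds of 2 stays above 99% with 131 patients but falls from about 90% to about 77% with 45. A locked score tested in validation patients keeps the power stated in Section 3.5.7 for a given sample size. Enrollment is complete, so this affects analysis text only; Section 3.5 already requires changes of method to be listed and explained in the study report.

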Patients with PD-L1 expression level above the final cutoff point will be analyzed by dose/schedule, separately for the ipilimumab-refractory population and the ipilimumab-naïve population. Based upon current data from this trial indicating similar response rates between ipilimumab-naïve and ipilimumab-treated patients, an analysis will also be performed where the two populations are combined for a given dose/schedule or even across doses/schedules as appropriate. RR, DCR and other efficacy endpoints will all be compared by PD-L1 expression category (above or below cutoff). A multivariate logistic regression analysis will be conducted to further assess the cutoff point after adjustment of important baseline characteristics. Covariates in the regression model will include PD-L1 expression category (above cutoff, below cutoff or indeterminate), gender, age category (above or below median), ECOG performance status (0 or 1), LDH (\leq upper limit of the normal range OR $>$ upper limit of the normal range or unknown), baseline tumor volume (above or below median), number of previous systemic therapies ($<$ or \geq median) and other prognostic factors and predictive biomarkers as appropriate.

Indeterminate PD-L1 expression levels are presumed to be missing at random. Reasons of missing data will be listed and investigated. A supportive analysis will be conducted to include those patients suspected to violate the missing at random assumption. PD-L1 expressions levels for these patients will be conservatively imputed to appropriately penalize for possible informative missing data.

Part F 2L+ Patients

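### The supportive logistic model for the melanoma PD-L1 cutoff splits age, tumour volume and prior therapies at the median, which can leave residual confounding; linear terms would adjust better at the same cost in parameters.

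*Combined protocol and SAP*

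**What the plan says.** Section 3.5.5.4 sets out two steps for melanoma: estimate a PD-L1 cutoff in a training set, then proceed to "application of the cutoff point to prospectively test the biomarker hypothesis (i.e., formal validation of the cutoff point". Once fixed, "it will be applied to the analysis of randomized patients in Part B and Part D".

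Under Validation, two kinds of analysis by PD-L1 category follow. One is unadjusted: "RR, DCR and other efficacy endpoints will all be compared by PD-L1 expression category (above or below cutoff". The other is adjusted: "A multivariate logistic regression analysis will be conducted to further assess the cutoff point after adjustment of important baseline characteristics". The covariate list for the adjusted model includes "age category (above or below median), ECOG performance status (0 or 1" and "baseline tumor volume (above or below median), number of previous systemic therapies", the therapy count being split into below versus at or above the median. LDH is classified against its upper limit of normal. The list ends with "other prognostic factors and predictive biomarkers as appropriate", with no functional form given.

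No continuous version of these covariates and no sensitivity analysis on their form is planned. No alpha, power or decision rule is attached to the model. The formal biomarker alpha, 2.5% one-sided, belongs to the Kendall's tau concordance test (Sections 3.5.6 and 3.5.7).

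**The concern.** Dose and schedule are randomized in these cohorts, but PD-L1 status is not. PD-L1-high versus PD-L1-low is therefore an observational contrast, and adjustment is what protects it. Splitting a continuous covariate at its median treats everyone on the same side as exchangeable. If PD-L1 and response both still vary with the covariate within each half, that shared variation is attributed to PD-L1.

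The bias can go either way. If PD-L1-high patients have the more favourable covariate values, a PD-L1 effect is created or exaggerated. If they have the less favourable values, a real effect is hidden. Sections 1.3 and 3.1.1 report that high PD-L1 goes with poor prognosis in several other cancers. That makes an association with prognostic covariates plausible, but does not give its size or sign in melanoma.

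At stake is how far the adjusted odds ratio can be relied on as evidence that the cutoff holds after allowing for baseline differences.

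**Working it through.** **No figure to reproduce for this model.** The documents give it no power or error rate. As a check on the validation-set inputs, the exact binomial calculation in Section 3.5.7 for the PD-L1-high group (10% versus 30% response, one-sided 2.5%) gives 78.8% at n=32 (at least 8 responses) and 94.3% at n=48 (at least 10). The plan states 79% to 94%, so these agree.

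**Inputs from the documents.** Planned sizes (Sections 1.5 and 3.5.7) are 88 in Part D, 160 ipilimumab-refractory (80 + 80) and 230 in the Q3W versus Q2W cohort. Pooled, 160 + 88 = 248 and 248 + 230 = 478. PD-L1-high prevalence is projected at 40% to 60%; 50% was used. The overall response rate was set at 30%.

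**Assumptions not in the documents.** These are the correlation between PD-L1 and each covariate, the covariate's effect on response, and a linear effect on the logit scale.

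**What a median split keeps.** For a normal covariate the squared correlation with its own median split is 2/π = 0.64. The other 1 − 0.64 = 0.36 of its variance is left unadjusted.

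**One confounder, two-sided 5% test, no true PD-L1 effect.** The correlation is 0.2 to 0.4 in size and the log-odds 0.6 to 1.0 per SD (odds ratios exp(0.6) = 1.8 to exp(1.0) = 2.7), acting so that the bias favours PD-L1.

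| | Median split | Linear term |
|---|---|---|
| PD-L1 odds ratio, n=88–478 | 1.07–1.28 | 0.99–1.01 |
| Error, n=88 | about 5–6% | about 4–6% |
| Error, n=160 | about 5–9% | about 4–6% |
| Error, n=478, strongest setting | about 16% | about 4–6% |

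**One or three aligned confounders, one-sided 2.5% test, 1,500 runs per cell.** Error with median splits:

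| Setting (odds ratio per SD) | N=160 | N=248 | N=478 | Spurious PD-L1 OR |
|---|---|---|---|---|
| One, r=0.2, OR 1.7 | 4.1% | 4.3% | 5.1% | about 1.06 |
| One, r=0.3, OR 2.2 | 6.3% | 6.5% | 9.5% | about 1.13 |
| Three, r=0.1, OR 1.7 | 4.3% | 4.5% | 5.7% | about 1.1 |
| Three, r=0.2, OR 1.7 | 7.3% | 9.5% | 13.9% | about 1.2 |
| Three, r=0.3, OR 2.2 (extreme) | 16.1% | 23.9% | 38.1% | about 1.5 |

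At zero correlation the median-split error is 1.9% to 2.6%, so there is no inflation. With linear terms it is 1.7% to 3.4% in every cell. The simulation standard error is √(0.025 × 0.975 / 1,500) = 0.4 percentage points.

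The splits still do most of the work. For three confounders at r=0.2, OR 1.7 and N=248, the error is 34.5% unadjusted, 9.5% with splits and 2.9% with linear terms.

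**Prior therapies.** Ipilimumab-naïve patients may have had 0 to 2 prior regimens (Section 2.2), so this split loses less than a split of age or volume. If the median in a subgroup were 0, however, the below-median group would be empty and there would be no adjustment for it.

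**The case against.** The strongest reply is about role. The model only further assesses the cutoff. A reader might infer that formal validation is biased, or that the plan's 2.5% biomarker error is inflated. The documents do not support that: the alpha belongs to Kendall's tau, which uses no covariate split, and nothing in the plan turns on a p-value from this model. That objection stands, and the point is confined to a supportive analysis.

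Second, the size rests on assumed correlations and effects, and the simulations generate a linear response, which suits the linear fix. When response instead steps at the median, the split gives an odds ratio of 1.00–1.03 and two-sided error of 4.5–5.6%, though the linear term also does well there. This stands as a limit on size. A reader might infer that a false PD-L1 effect will occur; the evidence shows only that it can.

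Third, a reader might take the LDH wording to mean that unknown values are merged with elevated ones. The text can equally be read as a separate third level, like the indeterminate level for PD-L1 in the same sentence, so no criticism is made on LDH.

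Fourth, the change is late. Enrolment is complete (Section 1.5), and Section 3.1.3 already reports dose-comparison findings from the randomized melanoma cohorts. Calling the change free would be wrong. Flexible terms also cost parameters: Part D at 30% response has 88 × 0.30 ≈ 26 responders for roughly eight parameters. Both points shape the fix.

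Last, the median is an outcome-blind rule, so its moving with the sample is a minor issue. It can still mean different things in the refractory, naïve and combined analyses.

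**Conclusion.** The point holds as a modest criticism of a supportive model. Three numeric covariates are dichotomised at the sample median in the only adjusted analysis of the melanoma cutoff. A model using the same data and the same number of parameters removes the residual confounding when effects are close to linear on the logit scale.

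The harm is conditional on PD-L1 being associated with a covariate that also predicts response. For one such covariate of moderate strength the excess error is small at the sizes of the separate cohorts. It grows with sample size, so it matters most in the combined analysis, and it becomes large only with strong or several aligned confounders.

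**What to change.** In Section 3.5.5.4, replace the three median splits with linear terms for age, log baseline tumour volume and the number of previous systemic therapies. Each uses one degree of freedom, as now, so the burden on the smaller cohorts does not rise. Reserve a prespecified restricted cubic spline for tumour volume for the larger pooled analysis. State that the model is supportive, and keep the prespecified median-split model as a sensitivity analysis reported beside it.

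The cost is a change of wording and a second model fit, with no new data. The downside is a late change to a prespecified model. Section 3.5 requires changes of method to be listed in the CSR with when and why they were made, and this one should be recorded there.
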